6.4 Dose modification of Sacituzumab Govitecan

The current established dose schedule for Sacituzumab Govitecan is 10 mg/kg on days 1 and 8 repeated every 21 days given as an intravenous infusion at the rates described in Section 6.3.3. There should be a minimum of 14 days between the day 8 infusion and the day 1 infusion of the next cycle in the absence of progression of disease or unacceptable toxicity. Planned deviations in treatment schedule are allowable up to 7 days due to holidays, vacations or personal reasons. The protocol allows aggressive medical management of patients in order to avoid dose reduction and dose delay as much as possible. Growth factors should be initiated once the ANC starts decreasing and may be used prophylactically as clinically indicated. In patients who would be considered high risk for neutropenia (those who experienced febrile neutropenia or Grade 3-4 neutropenia with prior treatments), use of growth factors should be initiated early on and used prophylactically as early as Cycle 1. Growth factors are required at cycle 1 for all patients \geq 65 years old.

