2. OBJECTIVES

2.1 Primary Objective

- To determine the proportion of subjects who have ≥50% PSA decline at or within 9 weeks of starting treatment with Sacituzumab Govitecan.
- To determine the 6-month rPFS rate

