ECOG performance status assessments (Appendix A) are required to assess subject functional status for study eligibility purposes and will be performed throughout the study according to the schedule of procedures.

5.2.7 *ECG*

A 12-lead ECG will be obtained at screening and at the end of study visit. It is not necessary to do ECGs 5 minutes apart. Additional unscheduled 12-lead ECG may be conducted when necessary at the investigator's discretion.

5.3 *Determination of Extent of Metastatic Disease*

All subjects will undergo an extent of disease evaluation consisting of bone scintigraphy, CT of the chest, CT of the abdomen and pelvis, and other regions of known/suspected involvement, at Screening unless already conducted within 30 days of Cycle 1, Day 1. CT scans should be performed with contrast unless contraindicated. MRI abdomen and pelvis with contrast may be done in situations where a CT with contrast is equivocal or contraindicated. A non-contrast chest CT should be done for subjects requiring an MRI of the abdomen and pelvis.

Subjects will undergo repeat evaluations of their extent of disease every 9 weeks (\pm 7 days) if they remain progression- free on study. Imaging modality should remain consistent by lesion throughout the study.

5.4 *Laboratory Evaluations*

On treatment days, blood samples should be collected prior to infusion. Laboratory tests will be performed by local labs and will include:

5.4.1 *CBC*

A CBC will consist of determinations of hemoglobin (HGB), hematocrit (HCT), white blood cells (WBC), red blood cells (RBC), neutrophils, lymphocytes, monocytes, eosinophils, basophils, and platelet count. Absolute values are preferred.

5.4.2 *Coagulation factors*

Partial thromboplastin time (PTT) and prothrombin time (PT) or international normalized ratio (INR) will be obtained according to the schedule of procedures and at any other visit where clinically indicated.

5.4.3 *Comprehensive metabolic panel (CMP)*

A CMP will consist of determinations of sodium, potassium, chloride, bicarbonate, blood urea nitrogen (BUN), glucose, creatinine, aspartate transaminase (AST), alanine transaminase (ALT), alkaline phosphatase, lactate dehydrogenase, total bilirubin, total protein, albumin, serum calcium, magnesium, and phosphorous.

5.4.4 *Urinalysis*

Urinalysis will include pH, specific gravity, and hemoglobin, glucose, ketones, and protein by dipstick, with microscopic exam if any of the dipstick analytes are 2+ or higher.

5.4.5 *PSA*

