- Treatment delay for any reason > 3 weeks (Treatment delays of up to 3 weeks will be allowed at the investigator's discretion). If treatment delay is due other than to treatment-related toxicity and a patient is receiving clinical benefit, the subject may be allowed to remain on study after > 3 weeks treatment delay after first obtaining approval from the Sponsor Investigator. The maximum treatment delay allowed even when the subject is receiving clinical benefit is no more than 6 weeks.
- Development of an intercurrent medical condition and need for prohibited concomitant treatment that precludes further participation in the study.
- Subject failure to follow study requirements.
- Physician decision: the investigator removes the patient from the study in the best interest of the patient.
- The subject is lost to follow-up.
- Study termination by the Sponsor.
- Use of prohibited concomitant medications (defined in Section 6.5.1).
- The subject may withdraw from the study at any time for any reason.

If a subject voluntarily withdraws from the study, attempts should be made to contact the subject to determine the reason(s) for discontinuation. All procedures and evaluations required by the End of Treatment Visit should be completed in the event of early withdrawal, regardless of reason. All subjects who discontinue the study due to an AE must be followed until resolution or stabilization of the AE.

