- c. ALT or AST >3x ULN and total bilirubin >2x ULN or INR >1.5

Patients with life threatening, grade 3 non-hematologic toxicity regardless of relationship to study drug should discontinue study treatment permanently. Examples include myocardial infarction or stroke.

In the event of other Grade 3 treatment-related toxicity at the time of a scheduled treatment day, the dose will be held and subjects will be assessed at least weekly. If recovery to \leq Grade 1 delays the next dose by only one week, treatment may resume then without dose reduction. If recovery to \leq Grade 1 delays the next dose by 2 or 3 weeks, treatment must be resumed at a reduced dose (Table 7). If treatment on day 8 of a cycle is held, the dose should be skipped and treatment resumed with day 1 of the following cycle. If treatment on day 1 is delayed, the entire cycle should be delayed, maintaining the same cycle number. The use of prophylactic G-CSF in subsequent cycles is recommended to prevent recurrence of neutropenia that would require a dose reduction. If recovery to \leq Grade 1 requires more than a three-week delay, treatment must be permanently discontinued.

After **cycle 1 day 1** treatment initiation should be withheld until ANC is $> 1000 / \mu\text{L}$. If day 8 is held for ANC $< 1000 / \mu\text{L}$, that dose will be missed. Resume dosing with next cycle. If delay more than 4 weeks, discontinue treatment. GCSF prophylaxis prior to cycle 2 is recommended if clinically appropriate.

For grade ≥ 3 neutropenia (ANC $< 1000 / \mu\text{L}$) after cycle 1 day 1 or after day 1 of subsequent cycles, hold day 8, initiate growth factor support and administer prophylactic growth factors with each subsequent cycle. Resume dosing with the next cycle only if toxicity resolves. **In subsequent treatment cycles**, treatment initiation for Day 1 of the cycle should be withheld until ANC $> 1000 / \mu\text{L}$ and GROWTH FACTORS should be used as clinically indicated. Patient will be assessed weekly for grade 3 ANC (ANC $< 1000 / \mu\text{L}$ to $500 / \mu\text{L}$) and bi-weekly for grade 4 ANC (ANC $< 500 / \mu\text{L}$). If delay more than 3 weeks, discontinue. Resume dosing at the next cycle if toxicity recovers to \leq grade 2 within 3 weeks. All subsequent cycles should be administered with growth factor support.

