APPENDIX B: STUDY CALENDAR

	Screening	Cycle 1		Cycle 2		Cycle 3			Cycle 4+		End of Treatment /Progression	Follow-up ⁷
	Within 30 days prior to C1D1	Day 1 (±3)	Day 8 (±3)	Day 1 (±3)	Day 8 (±3)	Day 1 (±3)	Day 8 (±3)	Day 15 (±7)	Day 1 (±3)	Day 8 (±3)	30 days from last treatment (+7)	Every 3 months (±7)
Assessments												
Medical History & Comorbidities	X	X		X		X			X			
Consent	X											
Physical exam and ECOG PS	X	X		X		X			X		X	
Toxicity assessment		X	X	X	X	X	X		X	X	X	
Concomitant medications	X	X	X	X	X	X	X		X	X	X	
Vital signs, height, weight ¹	X	X	X	X	X	X	X		X	X	X	
ECG	X										X	
Laboratory Evaluations												
PSA	X	X	X	X		X			X		X	X
Testosterone	X											
CTCs & plasma	X	X	X	X		X			X ²		X	
Buffy coat	X											
CBC with differential ⁹	X	X	X	X	X	X	X		X	X	X	
CMP ³	X	X	X	X	X	X	X		X	X	X	
PT/INR and PTT	X						X					
Urinalysis ⁴	X											
Treatment-Experimental Interventions												
Sacituzumab Govitecan		X	X	X	X	X	X		X	X		

Metastatic Biopsy ⁵	X							X				
Imaging studies												
^{99m} Tc-MDP bone scan ⁶	X							X ²		X ⁸		X
CT Chest; CT or MRI Abdomen/Pelvis ⁶	X							X ²		X ⁸		X

¹Height is only required during screening. BP and pulse prior to first infusion, every 15 for the first hour and then every 30 minutes until completing IV administration, at completion, and then additionally 30 minutes later. In absence of significant changes, frequency may be reduced with subsequent doses to prior to infusion, at 30 minutes, and then at completion. All time points may be collected \pm 5 minutes.

²Every 3 cycles (cycle 7, cycle 10, etc.) or every 9 weeks; if a cycle is delayed, procedures should still be performed every 9 weeks.

³Sodium, potassium, chloride, bicarbonate, BUN, glucose, creatinine, AST, ALT, alkaline phosphatase, lactate dehydrogenase, total bilirubin, total protein, albumin, serum calcium, magnesium, and phosphorous

⁴To include pH, specific gravity and hemoglobin, glucose, ketones, and protein by dipstick, with microscopic exam if any of the dipstick analytes are 2+ or higher.

⁵Fresh or Archived tumor from standard of care biopsy from metastatic site required for enrollment. On study biopsy at cycle 3 day 15 should be performed, regardless of treatment delays, to be performed in line with CT and bone scans.

⁶Window extended to \pm 10 days for scans.

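### Section 6.4's 14-day minimum before the next Day 1 is not carried into Appendix B's ±3-day infusion windows

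*Combined protocol and SAP*

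**What the plan says.** Section 6.4 gives the dose schedule as "10 mg/kg on days 1 and 8 repeated every 21 days" and then states: "There should be a minimum of 14 days between the day 8 infusion and the day 1 infusion of the next cycle". The sentence after that adds a separate tolerance: "Planned deviations in treatment schedule are allowable up to 7 days due to holidays, vacations or personal reasons". It does not say in which direction, or whether the 14-day minimum still applies.

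Appendix B heads every Day 1 and Day 8 column, from Cycle 1 through Cycle 4+, with a ±3 window. The Sacituzumab Govitecan row is marked under those columns, so the window covers dosing as well as assessments. Section 6.3.1 sends the reader to Appendix B for the schedule. None of the nine footnotes restricts infusion timing, although footnote 6 does alter the window for scans. No text says which rule governs when the two differ.

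**The concern.** A window on an infusion visit normally tells a site which days are acceptable for dosing. Here, when Day 8 is given on time, the entire early half of the next Day 1 window falls short of the stated minimum. The same infusion can be acceptable under Appendix B and too early under Section 6.4.

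Two things are at stake. The first is the rest period of a drug whose most likely toxicities, according to Section 6.4.1, are gastrointestinal and hematologic. The second is consistent classification. The trial is multicenter, Section 9.7 requires departures from the protocol to be documented, and Section 9.8 has monitors review compliance. Sites and monitors could record the same dosing date differently.

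**Working it through.** **Inputs.** Infusions on Days 1 and 8 of a 21-day cycle, and a 14-day minimum (Section 6.4); a window of ±3 days on each infusion visit (Appendix B).

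**Nominal gap.** The next Day 1 is Day 22, so the gap is 22 − 8 = 14 days. This equals the minimum exactly.

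**Gap with windows.** Let e be the Day 8 offset and n the next Day 1 offset, each a whole number from −3 to +3, with both visits counted from the same anchor:

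gap = (22 + n) − (8 + e) = 14 + n − e

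- Day 8 on time (e = 0), Day 1 early: n = −1, −2, −3 gives 13, 12, 11 days.
- Day 8 late, Day 1 on time (n = 0): e = +1, +2, +3 gives 13, 12, 11 days.
- Both extremes (e = +3, n = −3): 14 − 3 − 3 = 8 days.
- Opposite extremes (e = −3, n = +3): 14 + 3 + 3 = 20 days.

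Of the 7 × 7 = 49 offset pairs, 21 fall below 14 days (8 to 13), 7 equal 14 and 21 exceed it. These are counts of combinations, not expected frequencies.

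**Can both rules be met?** The gap is at least 14 when n ≥ e:

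| Day 8 offset | Permitted next Day 1 offsets | Days left in window |
|---|---|---|
| −3 | −3 to +3 | 7 |
| −2 | −2 to +3 | 6 |
| −1 | −1 to +3 | 5 |
| 0 | 0 to +3 | 4 |
| +1 | +1 to +3 | 3 |
| +2 | +2 to +3 | 2 |
| +3 | +3 only | 1 |

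The total is 7 + 6 + 5 + 4 + 3 + 2 + 1 = 28 pairs. Every Day 8 offset leaves at least one permitted Day 1.

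**Dependence on the anchor.** Suppose instead that Day 8 is counted from an actual Day 1 given s days off schedule, while the next Day 1 stays on the fixed calendar. Then gap = 14 + n − s − e, and s = e = +3 with n = −3 gives 14 − 9 = 5 days. The documents do not say which anchor applies, so the 8-day figure is conditional. The 11-to-13-day result for an early Day 1 needs only that the current cycle's Day 1 and Day 8 were on schedule.

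**The 7-day allowance.** If it were used to give Day 8 seven days late while the next Day 1 stayed at Day 22, the gap would be 14 − 7 = 7 days. A Day 8 held for toxicity does not create this case, because Section 6.4.1 has that dose skipped.

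**The case against.** The strongest reply is that two limits conflict only if they cannot both be satisfied, and here they can. Section 6.4 sets a specific floor on one interval; the ±3 is a general column heading in a table of assessments. Reading the specific floor as limiting the general window is the ordinary reading. This stands, and it rules out the stronger inference that the schedule is self-contradictory or unworkable. What remains is that the reader has to infer the precedence, and that the calendar, which sites work from, shows days that the floor excludes.

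The second reply is that laboratory and toxicity holds already protect subjects. "On treatment days, blood samples should be collected prior to infusion" (Section 5.4). Section 6.4.1 says that "treatment initiation for Day 1 of the cycle should be withheld until ANC" exceeds 1000/µL, and Grade 3 treatment-related toxicity on a treatment day holds the dose. Section 6.4 also requires growth factors at Cycle 1 for subjects aged 65 or over. This too stands and keeps the harm small. It does not replace the interval: after Cycle 1 Day 1, a subject with Grade 2 gastrointestinal toxicity, or a neutrophil count just above 1000/µL, is not stopped by those holds.

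Third, the 7-day allowance most naturally means delay, and a delayed Day 1 lengthens the gap. Section 5.8 also says "Treatment delays of up to 3 weeks will be allowed", so a holiday delay of a week fits without further text. That is right. Only a late Day 8 could shorten the gap, and a short parenthesis in the footnote covers it.

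**Conclusion.** The point holds as a minor dosing-safety inconsistency: a stated rest-period minimum is not reflected in the printed infusion windows. With Day 8 on time the shortfall is 1 to 3 days; using both windows under a shared anchor it is at most 6 days (14 − 8).

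Three larger conclusions might be drawn and are not supported.

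- *That subjects will often be dosed too early, or that a shorter gap raises neutropenia by a known amount.* The pair counts are not frequencies. Table 2 in Section 1.3 gives treatment interruptions by dose level, not by dosing interval, so the effect of a shorter gap cannot be sized.
- *That the statistical design is affected.* The sample-size argument in Section 8.3 does not use the dosing interval. Type I error, power and the 45 evaluable subjects are unchanged.
- *That the primary endpoint, "PSA decline at or within 9 weeks of starting treatment with Sacituzumab Govitecan", is put at risk.* Cycle 4 Day 1 falls nominally on day 1 + 3 × 21 = 64. A PSA drawn late at that visit would come from the upper side of the window (+3), which neither this gap nor its remedy changes. It is a separate question.

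**What to change.** Add one footnote to the Sacituzumab Govitecan row of Appendix B:

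*From Cycle 2 onward, the Day 1 window is subject to Section 6.4: Day 1 may not be given earlier than 14 days after the actual Day 8 infusion (including when Day 8 is moved under the 7-day allowance). If Day 8 was skipped, ±3 applies, subject to Section 6.4.1.*

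Because the floor runs from the actual Day 8 infusion, it holds whichever anchor a site uses for the windows. The Day 8 window and the +3 upper limit stay as printed, and under a shared anchor the in-window gap becomes 14 to 20 days.

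The cost is one footnote and some lost freedom to give Day 1 early. With Day 8 on time the Day 1 window becomes −0/+3. After a Day 8 at +3, only a Day 1 at +3 (Day 25) remains in window. A Day 8 moved by the full 7 days puts the earliest Day 1 at 15 + 14 = Day 29, outside the window and handled as a delay under Section 5.8.

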6.4.1 Dose reduction and termination guidelines

The most likely toxicities of Sacituzumab Govitecan are expected to be gastrointestinal symptoms and hematologic suppression. All subjects are closely monitored over the course of their treatment. NCI CTCAE v4.0 is used to grade all AEs and to provide the following dose reduction, delay or cessation guidelines in the event of treatment-related toxicity.

In this phase II study, subjects will receive 10 mg/kg Sacituzumab Govitecan once weekly for 2 consecutive weeks followed by 1 week rest in cycles of 21 days, with treatment continued in the absence of progression or unacceptable toxicity. Neutropenia, GI toxicity, fatigue and alopecia were the most common toxicities in phase I testing. All subjects will be closely monitored over the course of their treatment, with NCI CTCAE v4.0 used to grade all AEs and to provide dose reduction, delay or cessation guidelines in the event of toxicity.

On the first treatment day (Cycle 1 Day 1), if a subject experiences ANC $<1000/\mu\text{l}$ or \geq Grade 2 GI toxicity (disease related or from prior treatments), treatment initiation should be withheld until resolved to \leq Grade 1 or baseline level. It is recommended that growth factor support prophylaxis be administered to subjects who receive treatment and whose Cycle 1 Day 1 ANC is $<1500/\mu\text{l}$ and $\geq 1000/\mu\text{l}$.

If recovery to \leq Grade 1 or baseline level requires more than three-week delay, the subject should be withdrawn from the study.

Treatment will be permanently discontinued for a subject in the event of any \geq Grade 3 infusion reactions or for any Grade 2 immediate-type allergic/hypersensitivity infusion reactions (e.g., generalized urticaria, wheezing, hypoxia, dyspnea), which occur after pre-medication with antihistamines, H2 blockers and steroids.

Patients with grade 4 non-hematologic toxicity deemed at least possibly related must permanently discontinue the study drug except for the following situations:

- a. Chloride, bicarbonate, magnesium, phosphate or glucose abnormalities that last <72 hours, if not clinically complicated, and resolve spontaneously or respond to conventional medical interventions
- b. Amylase or lipase elevations that are not associated with symptoms or clinical manifestations of pancreatitis.

Treatment should be permanently discontinued if:

- a. ALT or AST >8x ULN
- b. ALT or AST >5x ULN for more than 2 weeks
- c. ALT or AST >3x ULN and total bilirubin >2x ULN or INR >1.5

Patients with life threatening, grade 3 non-hematologic toxicity regardless of relationship to study drug should discontinue study treatment permanently. Examples include myocardial infarction or stroke.

In the event of other Grade 3 treatment-related toxicity at the time of a scheduled treatment day, the dose will be held and subjects will be assessed at least weekly. If recovery to \leq Grade 1 delays the next dose by only one week, treatment may resume then without dose reduction. If recovery to \leq Grade 1 delays the next dose by 2 or 3 weeks, treatment must be resumed at a reduced dose (Table 7). If treatment on day 8 of a cycle is held, the dose should be skipped and treatment resumed with day 1 of the following cycle. If treatment on day 1 is delayed, the entire cycle should be delayed, maintaining the same cycle number. The use of prophylactic G-CSF in subsequent cycles is recommended to prevent recurrence of neutropenia that would require a dose reduction. If recovery to \leq Grade 1 requires more than a three-week delay, treatment must be permanently discontinued.

After **cycle 1 day 1** treatment initiation should be withheld until ANC is $> 1000 / \mu\text{L}$. If day 8 is held for ANC $< 1000 / \mu\text{L}$, that dose will be missed. Resume dosing with next cycle. If delay more than 4 weeks, discontinue treatment. GCSF prophylaxis prior to cycle 2 is recommended if clinically appropriate.

For grade ≥ 3 neutropenia (ANC $< 1000 / \mu\text{L}$) after cycle 1 day 1 or after day 1 of subsequent cycles, hold day 8, initiate growth factor support and administer prophylactic growth factors with each subsequent cycle. Resume dosing with the next cycle only if toxicity resolves. **In subsequent treatment cycles**, treatment initiation for Day 1 of the cycle should be withheld until ANC $> 1000 / \mu\text{L}$ and GROWTH FACTORS should be used as clinically indicated. Patient will be assessed weekly for grade 3 ANC (ANC $< 1000 / \mu\text{L}$ to $500 / \mu\text{L}$) and bi-weekly for grade 4 ANC (ANC $< 500 / \mu\text{L}$). If delay more than 3 weeks, discontinue. Resume dosing at the next cycle if toxicity recovers to \leq grade 2 within 3 weeks. All subsequent cycles should be administered with growth factor support.

In the event of neutropenia **grade ≥ 3** at the time of scheduled treatment day **despite growth factor prophylaxis**, resume treatment if the toxicity recovers to \leq grade 2 within 2 or 3 weeks with a 25% dose reduction for the first event (7.5mg/kg for a starting dose

of 10mg/kg). For subjects whose starting dose was 10mg/kg there will be a 50% dose reduction (5 mg/kg) for the second event that occurs while the patient is receiving prophylactic growth factors. Subjects will discontinue treatment for the 3rd occurrence while on growth factor support. NO DOSE REDUCTION IS REQUIRED IF TOXICITY RESOLVES WITHIN 1 WEEK.

Table 7. Dose Reduction Requirements for Severe Treatment-Related Toxicity

Event	Occurrence	Study Drug Dose
Grade 4 hematologic toxicity \geq 7 days OR Grade 3 febrile neutropenia (ANC < 1000/mm ³ , fever \geq 38.5°C), OR Grade 3 thrombocytopenia with clinically relevant bleeding OR Grade 4 thrombocytopenia, regardless of duration OR Any Grade 3 nausea, vomiting or diarrhea due to treatment, or other Grade 3 non-hematologic toxicity persisting $>$ 48 hours despite optimal medical management. OR At time of scheduled treatment, Grade 3 hematologic or Grade 3 non- hematologic toxicity which delays dose by 2 or 3 weeks for recovery to \leq Grade 2 or baseline.	First	7.5 mg/kg
	Second	5 mg/kg
	Third	Study drug will be discontinued
Hematologic toxicity: \leq Grade 1 (ANC \geq 1500/mm ³ or baseline level, Platelets \geq 75,000/mm ³ , or Hgb \geq 10.0 g/dL or baseline level); Grade 2 (ANC $>$ 1000/mm ³ , Platelets $>$ 50,000/mm ³ , or Hgb \geq 8 g/dL); Grade 3 (ANC < 1000/mm ³ , Platelets < 50,000/mm ³ , or Hgb < 8.0 g/dL); Grade 4 (ANC < 500/mm ³ , Platelets < 25,000/mm ³ , or Hgb < 6.5 g/dL).		
Note: In the event of adverse effects unrelated to study drug administration (both hematological and non- hematological adverse events), decision to dose delay or dose reduce is investigator discretion, based on the tolerability of the toxicities.		

The development of any of the severe toxicities noted in table 7 due to treatment requires permanent dose reduction for that subject by 25% of the assigned dose for first occurrence, 50% of the initial assigned dose for second occurrence. Subjects whose starting dose was 10mg/kg will discontinue treatment entirely in the event of a third occurrence (Table 7).

Do not re-escalate the Sacituzumab Govitecan dose after a dose reduction for toxicity has been made.

The dose guidelines will be followed with a goal of being able to give the first cycle without requiring dose reduction, delay, or discontinuation or cytokine support at the time the second cycle is given.

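### Section 6.4.1 permits full-dose resumption after a one-week hold for some Grade 3 events for which Table 7 requires a permanent 25% reduction

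*Combined protocol and SAP*

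**What the plan says.** Three pieces of Section 6.4.1 bear on this.

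- **General rule.** It opens "In the event of other Grade 3 treatment-related toxicity at the time of a scheduled treatment day". The dose is held. If recovery to Grade 1 or less "delays the next dose by only one week, treatment may resume then without dose reduction". A delay of two or three weeks makes a reduced dose mandatory, and that is the only place where the paragraph refers to Table 7. The rule is not confined to non-hematologic toxicity, since the same paragraph adds: "The use of prophylactic G-CSF in subsequent cycles is recommended to prevent recurrence of neutropenia that would require a dose reduction".
- **Table 7 and the sentence after it.** The table lists triggers joined by OR. Three Grade 3 triggers carry no delay condition: febrile neutropenia; "Grade 3 thrombocytopenia with clinically relevant bleeding"; and "Any Grade 3 nausea, vomiting or diarrhea due to treatment, or other Grade 3 non-hematologic toxicity persisting" for more than 48 hours under optimal management. Only the last trigger depends on timing: it covers Grade 3 "toxicity which delays dose by 2 or 3 weeks for recovery to" Grade 2 or less, or baseline. The sentence after the table says that developing any listed toxicity because of treatment "requires permanent dose reduction for that subject by 25% of the assigned dose for first occurrence". The second occurrence brings a 50% cut and the third brings discontinuation. Re-escalation is barred.
- **Capitalised waiver.** The paragraph on Grade 3 or higher neutropenia despite growth factor prophylaxis ends with a sentence in capitals that waives reduction when toxicity resolves within a week.

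**The concern.** The general rule and the event-based triggers in Table 7 can both apply to one event, and they lead to different doses. The word *other* at the start of the general rule sets it apart from the discontinuation rules just before it (for example life-threatening Grade 3 events). It does not set it apart from Table 7. Because the paragraph mentions Table 7 only for delays of two or three weeks, a site could reasonably conclude that the table does not come into play at one week.

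This is a multicenter trial, so two sites could treat the same event differently. One could give 10 mg/kg again and count nothing. The other could cut the dose permanently and count the first of three occurrences toward stopping. Under the lenient reading, a man whose event the protocol lists as requiring permanent reduction is given the full dose again.

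**Working it through.** The protocol states no figure to reproduce. The check sets the texts side by side, followed by arithmetic on dose and scale.

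**1. A case that meets both texts.** Take a man on 10 mg/kg with a first treatment-related Grade 3 diarrhea. It has lasted 4 days under optimal management, is present on Cycle 2 Day 1, and is down to Grade 1 one week later.

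| | General rule | Table 7 and the sentence after it |
|---|---|---|
| Condition met? | Yes: Grade 3, treatment-related, on a scheduled day, one-week recovery to Grade 1 | Yes: Grade 3 diarrhea due to treatment, more than 48 hours |
| Next dose | 10 mg/kg permitted | 10 × 0.75 = 7.5 mg/kg required, permanently |
| Occurrences counted | 0 | 1 of 3 |

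It does not matter whether the 48-hour qualifier also governs nausea, vomiting and diarrhea, because an event can last more than 48 hours and still recover within a week.

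**2. Where there is no conflict.** An event that meets only the last Table 7 trigger needs a delay of two or three weeks. For that trigger the general rule and the table agree that a one-week delay alone does not force a reduction.

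**3. Dose difference.** Section 6.3 uses a 70-kg subject as its example, with infusions on Days 1 and 8.

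- Full dose: 2 × 70 × 10 = 1400 mg per cycle
- Reduced dose: 2 × 70 × 7.5 = 1050 mg per cycle
- Difference: 350 mg, and 350/1400 = 25%

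**4. When the overlap can arise.** Section 6.4.1 says that a held Day 8 dose is skipped and treatment restarts with Day 1 of the next cycle. The one-week resumption therefore applies mainly to Day 1 holds. Section 6.4 requires at least 14 days between the Day 8 infusion and the next Day 1. If Day 8 was given, the event must still be Grade 3 about two weeks later and then recover to Grade 1 or less within a further week.

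**5. Scale.** Table 3 in Section 1.3 covers 420 patients, all causalities. As its columns are labelled, 18 had febrile neutropenia of Grade 3 or higher, of which 5 were Grade 4 and none Grade 5. Both rules concern Grade 3, so the relevant count is 18 − 5 = 13.

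- Grade 3 febrile neutropenia: 55 × 13/420 = 1.7 men

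The other Table 3 rows that bear on the non-hematologic trigger show no Grade 4 or 5 events:

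- Diarrhea: 55 × 37/420 = 4.8
- Nausea: 55 × 22/420 = 2.9
- Fatigue: 55 × 41/420 = 5.4

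Table 3 has no row for thrombocytopenia. These are expected counts before any overlap condition. The categories can share patients and should not be added. The event must also be treatment-related, be present on a scheduled day (mainly Day 1), recover within one week and, where the qualifier applies, have lasted more than 48 hours. The documents give no share meeting all of these, so no overlap count is offered.

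**The case against.** The strongest reply is that the texts can be obeyed together. The general rule only says that treatment *may* resume unreduced, whereas Table 7 is headed as a set of requirements and the sentence after it is mandatory. A site that cuts to 7.5 mg/kg breaches neither text; a site that gives 10 mg/kg breaches the later and more specific one. The layout of Table 7 supports this: its last trigger mirrors the general rule, and the event triggers can be read as standing independently. On this view only a cross-reference is missing.

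Much of this stands. It is the better reading, and it sets the direction of the fix. But it remains an inference. No sentence gives Table 7 precedence, the general rule cites the table only for longer delays, and Section 6.4 says that medical management aims to avoid reductions where possible.

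The reply is also right that the overlap is narrow, for the Day 1 reason shown in the working.

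A reader might be tempted by stronger readings that the documents do not support:

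- **That the capitalised waiver overrides Table 7 for every toxicity.** It closes a paragraph on neutropenia despite prophylaxis. It clouds only febrile neutropenia in men on growth factors, a group that includes all men aged 65 or over at cycle 1 (Section 6.4).
- **That about 2.4 men with febrile neutropenia are at issue (55 × 18/420).** That figure includes Grade 4 events, which neither the one-week rule nor this Table 7 trigger addresses.
- **That one recovery threshold should replace the others.** The general rule asks for Grade 1 or less and the neutropenia paragraphs accept Grade 2 or less. The dose conflict gives no reason to change either.

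**Conclusion.** The conflict is real and limited. For three kinds of Grade 3 event, the general rule as written permits a dose that Table 7 does not allow. The consequence for a man affected is a 25% dose difference, permanent under Table 7, and one occurrence counted or not counted toward discontinuation.

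It is likely to affect few men, and the number cannot be derived from the documents. The expected counts assume that the Table 3 rates carry over to this population. Those rates come from patients with other tumors and several dose levels, so they give scale and not bounds. The worked doses assume a 10 mg/kg starting dose.

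A reader might infer that the trial's conclusions are at risk. Nothing in the documents supports that: sample size, power and significance level do not depend on this rule, and no effect on the PSA response rate or the 6-month rPFS rate is claimed. Nor do the documents show that full-dose resumption would be unsafe in general, since the general rule already requires recovery to Grade 1 or less. The point is a dosing instruction that should be settled because it concerns patient protection and is cheap to correct.

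**What to change.** Make two changes in Section 6.4.1.

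1. Extend the one-week permission in the general rule with: *unless the event also meets another Table 7 criterion, in which case the Table 7 dose reduction and occurrence count apply*.
2. State that the capitalised one-week waiver applies only to neutropenia that meets no other Table 7 criterion.

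Leave the recovery thresholds unchanged: Grade 1 or less in the general rule, Grade 2 or less in the neutropenia paragraphs. The one-week permission keeps its purpose, for example for uncomplicated Grade 3 neutropenia.

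If the sponsor instead intends full dose after any one-week recovery, that exception should be written into Table 7.

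The cost is two amended sentences, with no new data, visits or subjects. The downside is possibly a few more dose reductions than under the lenient reading.
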